8.1 Definition of Protocol Deviations and Analysis Sets

Important protocol deviations are protocol deviations that might significantly affect the completeness, accuracy, and/or reliability of the study data or that might significantly affect a subject's rights, safety, or well-being. Important protocol deviations are defined in a separate document (latest version of MS200527-0018_List_of_IPDs).

All deviations will be identified and confirmed prior to or at the Data Review Meeting (DRM), which will occur before the database lock, including clinically important deviations leading to the exclusion of a subject from Per-Protocol (PP) analysis set (see Section 8.2).

The outcome of the DRM will document the important protocol deviations as well as the finalization of the analysis populations in a memo. Important protocol deviations will be documented in Clinical Data Interchange Standards Consortium Study Data Tabulation Model (SDTM) whether identified through sites monitoring, medical review and/or programming.

8.2 Definition of Analysis Sets and Subgroups

8.2.1 Sample Size

A sample size of 103 evaluable subjects per group provides 80% power at the $\alpha = 0.025$ one-sided significance level to detect

- an absolute improvement of 20% in Week 52 SRI-4 response proportion for M2951-treated subjects relative to placebo-exposed subjects, among subjects with SLEDAI-2K total score ≥ 6 at Screening, assuming a placebo response proportion of 40%,

or

- an absolute improvement of 25% in Week 52 SRI-6 response proportion for M2951-treated subjects relative to placebo-exposed subjects, among subjects with SLEDAI-2K total score ≥ 10 at Screening (i.e., HDA), assuming a placebo response proportion of 30%,

assuming that each two-primary endpoint is tested via a chi-squared test of the odds ratio (OR) for treatment effect at the 0.0125 one-sided level, and assuming that approximately 50% of randomized subjects are in the HDA group. If the absolute improvement in Week 52 SRI-6 response proportion in HDA subjects is only 20%, the power is 76%. Approximately 108 subjects will be randomized per treatment group to protect against a loss of information due to drop-out (for reasons other than efficacy/safety) of 5% over 52 weeks. Given the randomization ratio 1:1:1:1, the total sample size required for the PA is planned to be 432 subjects.

CCI

CCI

- a total evaluable sample size of 412 (i.e., 309:103 randomization for M2951:placebo) is involved in analysis of the two regions,

and applying “Method 2” from the PMDA Guidance, 32 evaluable subjects in the Japan cohort are required so that both observed region-specific effect sizes exceed 0.04 with probability of 80%. Taking into account a loss of information due to 5% drop-out at Week 52, for reasons unrelated to efficacy or safety, the total number of Japan subjects to be randomized is 36, or 8.3% of the total planned enrollment of 432.

CCI

8.2.2 Analysis Sets

Table 3 provides the definitions of the Analysis Sets and their purposes.

[figure not shown]
The analysis sets for PA will be drawn from all subjects randomized as of November 28, 2018 (n = 469), see Sections 6.2 and 7. Subjects not randomized (screen failure) will be included in PA analysis set if their screening date is on or before November 28, 2018. For the LTE analysis, the analysis sets will be drawn from all subjects who enter the LTE.

For analysis on HDA subpopulation, all subjects with SLEDAI-2K ≥ 10 at Screening will be included. The corresponding analysis sets will be drawn as specified above depending on the analysis (PA, LTE analysis).

Table 3: Analysis Sets

Analysis Set	Definition	Purpose
Enrolled	The Enrolled analysis set will include all subjects who sign the informed consent form.	The purpose of this analysis set is to count how many subjects signed the informed consent

ITT (Intent-To-Treat) Analysis Set	The ITT analysis set will include all randomized subjects. Subjects will be analyzed according to randomization treatment.	The ITT will be used for demographic/baseline characteristics.
mITT (modified Intent-To-Treat) Analysis Set	The mITT analysis set will include all randomized subjects who have received at least one dose of IMP (evobrutinib or placebo) and have at least one Baseline and one post-Baseline disease assessment (among the following: SFI, SLEDAI-2K, PGA, BILAG 2004, CLASI). Subjects will be analyzed according to randomized treatment. Subjects with Protocol Deviation (PD) code equal to PDEV80 are excluded from mITT.	The mITT will be used for all efficacy endpoints. The mITT will be used for demographic/baseline characteristics in case more than 10% of ITT are excluded from mITT.
Safety Analysis Set (SAF)	The Safety analysis set will include all subjects who have received at least one dose of IMP (evobrutinib or placebo). Subjects will be analyzed according to the actual treatment they receive.	The SAF will be used for the analysis of medications, exposure/compliance and safety endpoints.
QoL (Quality of Life) Analysis Set	The QoL analysis set will include all ITT subjects who have received at least one dose of IMP (evobrutinib or placebo) and have at least one Baseline and one post-Baseline QoL assessment (among the following: SF-36, EQ-5D-5L, LupusQoL, PGIC, FACIT). Subjects will be analyzed according to randomized treatment. Subjects with PD code equal to PDEV80 are excluded from QoL.	The QoL analysis set will be used for the analysis of QoL data.
PP (Per-Protocol) Analysis Set	The PP analysis set will include all subjects from mITT who do not have any clinically important protocol deviations (see Section 10.2). Subjects will be analyzed according to randomized treatment.	The PP will be used for the two-primary and key secondary efficacy endpoints. Efficacy analyses on PP will be performed if at least 10% of the mITT are excluded from PP. Demographic/baseline characteristics analyses will be repeated for the PP if more than 10% of mITT are excluded from PP.

CCI

CCI

CCI

It has been notified to the Sponsor that medical/scientific misconduct occurred at sites 653 and 107 during the study. CCI. As a result, subjects who have been enrolled in such sites will be included in the SAF and ITT analysis sets but excluded from mITT (and therefore PP), QoL, CCI, CCI and CC analysis sets.

8.2.3 Subgroup Analysis

Table 4 below defines the subgroups to be used for subgroup analysis as described in Section 14 and Section 15.

Subgroup analysis on the stratification factors race (Black versus non-Black) and, disease activity prior to dosing on Day 1 (SLEDAI-2K total score < 10 versus ≥ 10 at Screening) will be defined using the eCRF data. The stratification factor region (US and Western Europe, Japan, and RoW) will be defined using Interactive Web Response System (IWRS) as only collected as part of randomization data.

Table 4: Subgroups and Strata

Subgroup	Content	Definition
A	Disease Activity at Screening (HDA) (stratification factor)	non-HDA: SLEDAI-2K total score < 10; HDA: SLEDAI-2K total score ≥ 10 (from SLEDAI1 form of the eCRF) Some analysis will be presented on HDA subpopulation (i.e. including all HDA subjects) as detailed in Sections 14 and 15.
B	Serological Activity status at Screening	Positive: positive anti-dsDNA (i.e. > 15 U/mL) OR complement levels (C3 or C4 below (<) LLN); Negative: otherwise, i.e. negative/indeterminate anti-dsDNA and C3/C4 complement levels above or equal (>=) LLN (from Central Laboratory: anti-dsDNA, serum C3 and serum C4)
C	Race (stratification factor)	Black or African American; other (from DEM form of the eCRF)
D	Region (stratification factor)	US and Western Europe; Japan; ROW (from IWRS)
E	Ethnicity 1	Hispanic/Latino VS Non-Hispanic/Latino (from DEM form of the eCRF)
F	Background Therapy of Immunosuppressant	Yes; No (derived from Concomitant Medication form of eCRF, using the L04A ATC code, see Section 14.1.2.2 for derivation detail)
IWRS = Interactive Web-Response System		

CCI [REDACTED]

Table 5: Exploratory Subgroups and Strata

Subgroup	Content	Definition
CCI	[Redacted]	[Redacted]
CCI	[Redacted]	[Redacted]

9 General Specifications for Data Analyses

All statistical analyses will be performed by PPD Inc., except the modeling and simulation analysis and the gene expression, which will be performed by Merck/EMD Serono or delegate.

CCI

9.1 Actual Treatment Assignment

A subject who received 2 different types of treatment regimen over the course of treatment should be tabulated according to the treatment regimen received most frequently. If there is a “tie”, the highest dose will be chosen.

9.2 Presentation of Tables/Listings/Figures (TLFs)

Tables and figures will be sorted by treatment group (in the order stated in Table 6) and chronological time point (where applicable).

Table 6: Treatment Groups and Regimens

Treatment Group	Regimen	Presentation for the PA	Presentation for the LTE analysis (*)
1	Placebo	Placebo	Placebo/Evobrutinib 50 mg BID
2	Evobrutinib 25 mg QD (once daily)	Evobrutinib 25 mg QD	Evobrutinib 25 mg QD/Evobrutinib 50 mg BID
3	Evobrutinib 75 mg QD	Evobrutinib 75 mg QD	Evobrutinib 75 mg QD/Evobrutinib 50 mg BID
4	Evobrutinib 50 mg BID (twice daily)	Evobrutinib 50 mg BID	Evobrutinib 50 mg BID/Evobrutinib 50 mg BID

(*): Subjects who complete the 52-week Double-blind placebo-controlled period will be offered participation in an optional open label, LTE period for an additional 2 years. During this LTE period, subjects will be administered evobrutinib at an initial dose of 50 mg BID or the eventual Phase III dose, when decided.

All data recorded during the trial will be presented in individual data listings (in the order stated in Table 6). All listings are sorted by treatment group, subject, and time point (where applicable), if not otherwise stated.

9.3 Data handling for the planned analyses

For the PA, data will be handled according to the corresponding Data Handling Report and Interim Database Lock Plan.

The stratification factors race (Black versus non-Black) and disease activity prior to dosing on Day 1 (SLEDAI-2K total score < 10 versus ≥ 10 at Screening) will be summarized using both the eCRF data and the IWRS data in demographics and baseline characteristics. However, for statistical analyses, eCRF data will be used. The stratification factor region (US and Western Europe, Japan, and RoW) will be defined using IWRS. (See Section 8.2.3, Table 4)

9.4 Presentation of continuous and qualitative variables

Continuous variables including CC but not CC will be summarized using descriptive statistics, i.e.,

- number of subjects (N)
- number and percentage of non-missing values
- number and percentage of missing values
- mean, standard deviation (SD)
- median, 25th Percentile - 75th Percentile (Q1-Q3)
- minimum and maximum

[figure not shown]
The number of digits for non-derived and derived data, presented in outputs or available in Analysis Data Model (ADaM) datasets, is specified in the Biostatistics Outputs Assembly (BOA) document. For efficacy endpoints from Section 14, median and SD will be presented with 1 more digit compared to the original data, whereas mean, min, max, Q1-Q3 will be presented with the same number of digits as the original data.

For both continuous and qualitative variables, percentages such as 0% or 100% should be reported with the same format used for the column, together with the count of observations. For example, if the count of observations is zero, then display '0 (0.0)'; if the count of observations represents 100%, then display 'xx (100.0)'.

Qualitative variables will be summarized by counts and percentages. Unless otherwise stated, the calculation of proportions will be based on the number of subjects in the analysis set of interest. Therefore, counts of missing observations will be included in the denominator and presented as a separate category.

In case the analysis refers only to certain visits, percentages will be based on the number of subjects in the analysis set of interest, unless otherwise specified. Total of missing and non-missing observations at each time-point will reflect the population still in the trial at that time. For example, if a subject is still in the trial at the time-point but with missing data, it should be counted in the number of missing observations.

CCI

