14.3.3 Disease activity over time

Table 23 provides details on disease activity endpoints.

Table 23 : Disease Activity Endpoints

Endpoint (*)	Analysis method	Data Handling Notes
CFB in SLEDAI-2K score	
 • Descriptive statistics for continuous variable, including absolute value, CFB and percent CFB 	As observed
CFB in CLASI-A score	
 • Descriptive statistics for continuous variable, including absolute value, CFB and percent CFB 	As observed
BICLA response	
 • Number and percentage of subject with response by each treatment group • Presentation of adjusted Odds-Ratio (OR), 2-sided 95% CI of OR, nominal p-value, adjusted p-value from Logistic Regression (same as primary analysis of primary endpoint) 	As primary analysis
CFB in BILAG-2004	
 • Descriptive statistics of total score, including absolute value at baseline and each post baseline visit, CFB and percent CFB at each post baseline visit 	As observed
CFB in PGA	
 • Descriptive statistics, including CFB and percent CFB for the PGA score as a continuous variable on a 0-3 scale 	As observed

(*) See Appendix 18.1 for definition of each endpoint.

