14.6 LTE Efficacy Endpoints

LTE efficacy endpoints will be analyzed on mITT for the LTE Analysis only.

Same methods of imputation used for the PA will be applied to LTE analysis. However, missing efficacy assessments collected after the announcement to the sites of study early termination (i.e. 23 March 2020) will not be imputed.

Table 25 summarizes the analyses that will be performed for each LTE endpoint.

For all LTE efficacy endpoints, the baseline from the 52-weeks treatment period will be used (e.g., SRI responses, change from baseline, etc.).

Institution of EAC-determined protocol-prohibited medication/treatment (i.e., EAC-treatment failure) as well as time to first flare/flare-free/AFR will be censored at the time of announcement to the sites of study early termination (i.e., 23 March 2020).

Table 25: Analysis of LTE endpoints

Endpoint	Method
SRI response over time	
SRI response rate will be summarized over time during LTE period. The baseline from the 52-week treatment period will be used (see Section 9.6).
 
The same analysis will be repeated for subjects with a gap greater than or equal to 2 weeks between 52-week and LTE treatment periods.
 
A line plot representing the SRI response rate over time will be also provided

Low disease activity status over time	Proportions of subjects with LLDAS, SLEDAI-2K \leq 2 or clinical SLEDAI-2K \leq 2 will be summarized over time.
Change over time in CLASI-A and SLICC/ACR Damage Index Score	Descriptive statistics will be presented over time for each endpoint.
Change over time in disease activity as measured by the BILAG, SLEDAI-2K, and PGA	Descriptive statistics will be presented over time for each endpoint.
BICLA response over time	Proportion of subjects with BICLA response will be summarized over time.
Change over time in prednisone-equivalent CS dose	Descriptive statistics will be presented as detailed in Section 14.3.5. This will be applied at LTE Week 24, Week 52 and Week 104.
CCI	

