18.1.1.10 Total and organ specific numeric scores

Attribution of numeric values to each grade (derived above) is as follow:

Table 32: BILAG scoring

Grade	Numeric value
A	12
B	8
C	1
D	0
E	0

The total score is calculated as the sum of the organ domain scores.

If at least one organ domain score is missing, then the Total score is missing.

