18.1.3 SLEDAI-2K

The Total score of the SLEDAI-2K is calculated as the sum of the weights of the descriptors marked as present by the investigator. The weights corresponding to each of the 24 descriptors are described in the table below:

Table 33: SLEDAI scoring

Descriptor	Weight
Seizure	8
Psychosis	8
Organic brain syndrome	8
Visual disturbance	8
Cranial nerve disorder	8
Lupus headache	8
Cerebrovascular accident	8
Vasculitis	8
Arthritis	4
Myositis	4
Urinary casts [#]	4
Hematuria [#]	4
Proteinuria [#]	4
Pyuria [#]	4
Rash	2
Alopecia	2
Mucosal ulcers	2
Pleurisy	2
Pericarditis	2
Low complement* [#]	2
Increased DNA binding* [#]	2
Fever	1
Thrombocytopenia [#]	1
Leukopenia [#]	1

*blinded descriptor

[#]laboratory components

Handling with blinded descriptor: As “Increased DNA binding” and “Low complement” are blinded items, the SLEDAI-2K total score will have to be derived for primary analysis with the laboratory unblinded values. “Increased DNA binding” item is defined as “>25% binding by Farr assay or above normal range for testing laboratory”. The parameter to take into account in laboratory data is “anti-Double Stranded DNA”. Increased DNA binding will be derived as ‘present’ if the anti-dsDNA value is positive (i.e. > 15 U/mL). “Low complement” item is defined as “decrease in C3 or C4 below the lower limit of normal for testing laboratory”. The parameters to take into account in laboratory data are “Complement C3” and “Complement C4”.

Total score used for statistical analysis will be re-calculated for all timepoints except screening and Day 1 with the unblinded values of Increased DNA binding and Low complement. The total score for the next visits as stated by the investigator in the eCRF will not be used in any statistical analysis.

Handling of missing items in SLEDAI-2K scores and change from baseline scores:

Actual scores

If the missing clinical component has weight > 4 in the overall score (see [Table 33](#)), then no imputation is performed. The SLEDAI-2K score will be missing.

If the missing clinical component has weight ≤ 4 in the overall score (see [Table 33](#)) or laboratory components missing, then the missing values will be imputed with the value of previous analysis visit. Only value assessed post-Day 1 dose (i.e. after baseline) can be used for imputation. If at least one item is still missing, then SLEDAI-2K score will be calculated based on available data.

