18.1.5 CLASI

Cutaneous Lupus Erythematosus Disease Area and Severity Index is a validated measurement instrument for lupus erythematosus developed for use in clinical studies that consists of separate scores for the activity of the disease (CLASI-A) and the damage done by the disease (CLASI-D).

The CLASI activity score is calculated on the basis of erythema, scale/hyperkeratosis, mucous membrane involvement, acute hair loss and non-scarring alopecia. The CLASI damage score is calculated on the basis of dyspigmentation and scarring, including scarring alopecia. Dyspigmentation due to lesions is defined as lesions that remain visible for more than 12 months, which are considered to then be permanent ([Albrecht 2005](#)).

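### Section 9.4 gives efficacy means no extra digit, so means of integer scores print as whole numbers and a displayed arm difference can be off by almost 1 point

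*SAP*

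**What the plan says.** SAP Section 9.4 refers the number of digits in general to another document (it "is specified in the Biostatistics Outputs Assembly (BOA) document") and then sets a specific rule for efficacy. The median and SD carry one extra digit. The other statistics, the mean among them, do not: "whereas mean, min, max, Q1-Q3 will be presented with the same number of digits as the original data". Nothing later in the SAP overrides this.

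The raw precision of the affected endpoints follows from their definitions:
- SLEDAI-2K total (Section 18.1.3): "calculated as the sum of the weights of the descriptors marked as present by the investigator". The 24 weights in Table 33 are 8, 4, 2 or 1.
- BILAG-2004 total (Section 18.1.1.10): "The total score is calculated as the sum of the organ domain scores". Table 32 assigns 12, 8, 1, 0 and 0 to grades A to E.
- SLICC/ACR Damage Index (Section 18.1.6): a sum of items scored 1, 2 or 3.
- Number of flares (Section 14.3.2.2): a count, summarised by mean, SD and median among other statistics.

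For change in SLEDAI-2K, Table 23 plans "Descriptive statistics for continuous variable, including absolute value, CFB and percent CFB"; the BILAG row is likewise descriptive only. For BILAG, SLEDAI-2K and SLICC/ACR in the extension, Table 25 says "Descriptive statistics will be presented over time for each endpoint". Flares in the extension are also described without modelling.

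**The concern.** The extra digit goes to the statistics that need it least. The median of whole-number scores is a whole number or ends in .5. The mean can take any value in between, yet it is grouped with the minimum, maximum and quartiles and gets no decimal. A table built to this rule would show a whole-point mean SLEDAI-2K change beside an SD with one decimal.

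For change in SLEDAI-2K and BILAG the printed mean is the main summary of average change, because no repeated-measures model is planned for them as it is for the quality-of-life scores. At stake is whether the report's tables give these secondary results accurately enough to compare arms.

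**Working it through.** The SAP states no figure for this rule that could be reproduced. The check is how far rounding to whole points can distort a displayed difference.

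**Inputs**
- Mean shown with no extra digit; median and SD with one (Section 9.4).
- SLEDAI-2K and BILAG totals are integers (Tables 33 and 32).
- 103 evaluable subjects per arm (Section 8.2.1), used only to set a scale.
- SD of SLEDAI-2K change: not in the SAP. Assumed range 3 to 6 points.

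**Step 1: examples.** True mean changes of -5.4 and -4.6 both print as -5, so the displayed difference is 0 instead of 0.8. True changes of -4.49 and -5.51 print as -4 and -6, so it is 2 instead of 1.02.

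**Step 2: how often a difference prints as 0.** Let two arm means differ by d, and let their position relative to the rounding grid be uniform. For d below 1, a rounding boundary falls between them with probability d. The displayed difference is then 1; otherwise it is 0. So P(shown as 0) = 1 - d for d < 1, and 0 for d ≥ 1. A simulation of 2,000,000 placements agreed:

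| True difference | Shown as 0 | Largest error |
|---|---|---|
| 0.2 | 80% | 0.8 |
| 0.5 | 50% | 0.5 |
| 0.8 | 20% | 0.8 |
| 0.9 | 10% | 0.9 |
| 0.99 | 1% | 0.99 |
| 1.2 | 0% | 0.8 |

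The error runs both ways: a true 0.2 that does not print as 0 prints as 1.

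**Step 3: scale against sampling error.** SE of a difference = SD × √(2/103).
- SD 3: 0.42; SD 4: 0.56; SD 5: 0.70; SD 6: 0.84.
- A difference of 0.99 point is therefore 0.99/SE = 2.4, 1.8, 1.4 or 1.2 standard errors.

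Rounding of up to almost 1 point is thus at least as large as the sampling error over the whole assumed range.

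**Step 4: small-valued endpoints.** A mean SLICC/ACR change below 0.5 prints as 0. Arms averaging 0.1 and 0.4 flares per subject (illustrative values) would both show a mean of 0.

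**Step 5: after the fix.** With one decimal for the mean, none of the tested differences (0.2 to 1.2) prints as 0, and the displayed difference is within 0.1 point of the true one.

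**The case against.** The strongest reply is that this is a display rule. No test, interval or patient-level derivation uses the rounded mean. SRI-4 and SRI-6 are derived from individual scores and analysed by logistic regression, and continuous quality-of-life scores get model-based means with intervals. That stands, and it limits the point to reporting.

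Several stronger readings are tempting and not supported:
- **That real arm differences vanish.** Only differences below 1 point can print as 0, and not all of them do.
- **That a difference of clinical size cannot be seen.** The SAP defines no group difference below 1 point as clinically meaningful. Its SLEDAI-2K change thresholds (4 or 6 points for SRI, 3 for a mild/moderate SFI flare) apply to individuals.
- **That readers cannot recover the value.** Section 9.2 plans individual listings of all recorded data, and the median, SD and quartiles are shown too. The loss affects those who have only the summary tables.
- **That CLASI-A is affected in the same way.** The SAP says "The CLASI activity score is calculated on the basis of erythema, scale/hyperkeratosis, mucous membrane involvement, acute hair loss and non-scarring alopecia" but gives no item scoring. Whole-number scoring would be an assumption, and the point does not need it.
- **That every extension efficacy score is affected.** PGA is on a continuous 0 to 3 scale, several extension endpoints are proportions, all groups receive 50 mg BID in the extension, and no modelling of these scores is planned there.

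The separate output-format document is not at hand and may settle what counts as raw precision for derived variables such as change from baseline. This leaves some doubt about the final print format, but the efficacy sentence in Section 9.4 is explicit and should not depend on another document to correct it.

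For flares in the primary analysis, a negative binomial rate ratio is planned, so the rounded mean count matters less there than in the extension.

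**Conclusion.** The point holds as a minor reporting defect. Followed as written, Section 9.4 prints means and mean changes of the SLEDAI-2K total, BILAG-2004 total, SLICC/ACR Damage Index and flare counts as whole numbers. For SLEDAI-2K and BILAG change, and for the integer scores in the extension, no planned model supplies a more precise figure. The summary tables can therefore hide a difference below 1 point or misstate a difference by up to almost 1 point.

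The percentages assume that the arm means fall uniformly relative to the rounding grid. The comparison with sampling error rests on an assumed SD of 3 to 6 points and on the planned 103 evaluable subjects per arm. The rounding bound itself needs neither assumption. There is no effect on type I error, power or the primary conclusion.

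**What to change.** In Section 9.4, present the mean of Section 14 endpoints with at least one more digit than the raw data, and the SD at least as precisely as the mean. Keep the minimum and maximum at raw precision. Whether the SD carries one or two extra digits is house style. State that the same precision applies to mean change from baseline, and align the output-format document.

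Apply the rule to the extension outputs still to be produced. SAP version 4.0 was written after the primary analysis results had been reviewed, so the Table 23 summaries may already exist. If they do, re-run the affected ones. That re-run is the only real cost; no analysis changes.
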